Effects of Reading to Preterm Infants on Baby and Parents' Well Being

ID: 2014-1464

10/24/19

Study Protocol:

Parents of infants born between 23 and 31 weeks gestational age who were between 260/7 and 346/7 weeks post menstrual age cared for in the NICU were approached for enrollment into the study. All infants were at least 7 days or older after birth to allow successful transition to extra uterine life. Parents agreed to participate and to read out loud from written word as a requirement for participation in the study. Infants were excluded if: they were considered too ill to participate by the primary care team, were on high frequency ventilation, were not expected to survive, had chromosomal anomalies, had abnormalities of the midface, or had a family history of/suspected congenital hearing loss. The study was approved by the Georgetown University Institutional Review Board. Of 21 sets of parents approached, 18 consented to participate. Two sets of parents decided to participate only with live reading and did not make a voice recording. Parents were given a children's book using a rhyming pattern of text to read, but other materials were allowed according to parental preference. Parents were asked to read or create a recording lasting a minimum of 15 min but up to 60 min of recorded reading. Mothers and fathers could read to their infants individually. Recordings were made using Garage Band® on a study computer and exported to bedside ipods®. Recording was played via humidity resistant Bluetooth enabled speakers in the incubator. Recorded reading was played for infants up to twice per day by the bedside nurse. The primary care team could withhold any recorded or bedside reading exposure if an infant was deemed too unstable for that experience on any given day. Live and recorded reading could occur on the same day with the goal of at least 2 reading episodes per day, but because parents may not be available for live reading everyday, recorded and live reading episodes may occur on different days. Cardiorespiratory events for each reading exposure were compared to the immediate period before and after the reading exposure. As such the period before each reading exposure served as the control period for that reading exposure to mitigate the effect of reading on different days or time periods. All infants were being cared for in incubators on reading exposure days. For 2 infants, at one time period each, the infant was removed from the incubator and was being held for all comparison time points around that single reading exposure. Two infants had one day of data when the infant was held only during reading exposure. Data from those days were excluded from analysis. For all other live reading exposures, the infant was in the incubator with parents reading through the open portholes. Sound decibel levels were checked via a sound meter (Triplet SoniChek TSC-MC1 Mini Digital Sound Level meter) to ensure sound levels did not increase above baseline if above 45 decibels prior to reading exposure.

Cardiorespiratory data, including heart rate (HR), respiratory rate (RR), oxygen saturation, apnea and bradycardia events, were continuously downloaded every 5 seconds directly from bedside GE monitors using BedMaster EX Software and exported to a spreadsheet for analysis. The data on mode of respiratory support and amount of supplemental oxygen needed were collected for each time period. Mean RR, HR, apnea and bradycardia episodes, amount of supplemental oxygen needed, mode of respiratory support, if any, and number of periods with oxygen saturation <85% were compared to the reading period at 3 time points: 3 h before reading, 1 h before reading and 1 h after reading. These time points were chosen to provide a variety of time periods in relation to care times and feedings, including

day and nighttime periods. Results were compared using χ^2 test for categorical variables and student's t test for continuous variables. $P < 0.05$ was considered as significant.

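### Comparison periods are not kept free of other readings, so some control time can itself be reading time; under assumed timing the dilution is small (about 1–4%, at most about 7–8%, of window time)

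*Combined protocol and SAP*

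**What the plan says.** All the relevant text is in the Study Protocol section of the combined document.

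- **Frequency.** "Live and recorded reading could occur on the same day with the goal of at least 2 reading episodes per day". The sentence continues that, because parents may be unavailable, "recorded and live reading episodes may occur on different days". Playback has its own ceiling: "Recorded reading was played for infants up to twice per day by the bedside nurse". A reading or recording lasts 15 to 60 min.
- **Who reads.** "Mothers and fathers could read to their infants individually".
- **Control.** "the period before each reading exposure served as the control period for that reading exposure".
- **Time points.** Outcomes in the reading period are compared with "3 h before reading, 1 h before reading and 1 h after reading". The stated reason is variety around care and feeding, including "day and nighttime periods". Other readings are not mentioned.
- **Exclusions to keep the periods comparable.** One is stated: "Two infants had one day of data when the infant was held only during reading exposure. Data from those days were excluded from analysis".

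The section does not say whether a time point such as 3 h before is a 3-h block or a shorter slot beginning 3 h earlier. It gives no reading times and no count of readings per day.

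**The concern.** The before/during/after contrast is the only one described; there is no unexposed group. It assumes that the comparison periods are time without reading. The plan intends more than one reading on many days and looks back as far as 3 h, but has no rule for a second reading inside a comparison period.

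Where that happens, reading is compared partly with reading. If the other reading acts like the index one, the observed difference shrinks in proportion to the share of the window it fills. In the after-reading period the same shrinkage could be mistaken for an effect that persists. The plan did remove days on which holding differed between the periods, so comparability was considered, but the exposure itself was not handled in the same way. Without a rule or a count of overlapped minutes, a reader cannot tell how much control time is affected.

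**Working it through.** The plan states no power, effect size or sample size calculation, so there is no figure of its own to reproduce. The check asks how much window time another reading would fill.

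**Inputs from the document.** Two readings a day (the goal); length L = 0.25 to 1 h; the three time points.

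**Assumptions, because the document is silent.** Start times are uniform over T = 12 to 24 h; the two readings have equal length and do not overlap; there is no carryover. A block is the whole hour or three hours next to the reading. A slot is a reading-length period that starts 3 h before, 1 h before, or 1 h after the reading.

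**Formula.** Let g be the gap between the two readings and M = T − L. Then g has density 2(M − g)/M² on 0 to M, and the other reading is on the relevant side with probability ½. With o(g) the overlap in hours and W the window length:

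share f = [1/(W·M²)] ∫ o(g)(M − g) dg

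**Worked cases.**

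- T = 24, L = 1 (M = 23, M² = 529), 3-h block: o = 1 up to g = 2, then 3 − g up to g = 3. The integral is 44 + 10.33 = 54.33, and 54.33/(3 × 529) = 3.42%.
- T = 24, L = 0.25 (M = 23.75, M² = 564.06), 1-h block: o = 0.25 up to g = 0.75, then 1 − g up to g = 1. The integral is 4.383 + 0.716 = 5.099, and 5.099/564.06 = 0.90%.
- T = 12, L = 1 (M = 11, M² = 121): 1-h block (5.5 − 0.167)/121 = 4.41%; 3-h slot 9/121 = 7.44%; slot starting 1 h after, 10/121 = 8.26%.

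**Share of window time that is another reading, L from 15 to 60 min:**

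| Window | 24-h spread | 12-h spread |
|---|---|---|
| 3 h before, block | 0.95–3.42% | 1.79–6.70% |
| 3 h before, slot | 0.93–3.97% | 1.63–7.44% |
| 1 h before, block | 0.90–2.14% | 1.79–4.41% |
| 1 h before, slot | 1.02–2.14% | 1.99–4.41% |
| 1 h after, block | 0.90–2.14% | 1.79–4.41% |
| 1 h after, slot | 1.01–4.16% | 1.95–8.26% |

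**Windows touched at all.** P = ½[1 − (1 − W/M)²] for a block. This is about 12% of 3-h blocks over 24 h and up to about 24% over 12 h, and about 4–9% of 1-h blocks. The average is therefore concentrated: when a 1-h block is touched, roughly 22% (0.90/4.1) to 51% (4.41/8.7) of it is reading.

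**Effect on the contrast.** If overlapped time carries the full reading effect, the contrast retained is 1 − f. From an assumed 80% power at two-sided 0.05, power = Φ(2.80(1 − f) − 1.96): f = 0.9% gives 79.3%; 4.0% gives 76.7%; 7.4% gives 73.7%; 8.3% gives 72.9%.

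**Other frequencies.** If half of reading days have one reading, two thirds of readings fall on two-reading days, so the before-window shares become about 0.6–5% (0.9 × 2/3 to 7.44 × 2/3). Three readings every day give, by simulation, about 2–8% over 24 h. The share reaches about 15% in the before windows only with 60-min readings within 12 h.

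**The case against.** The strongest reply is that nothing shows overlap occurred. The document is a short account in the past tense, and silence on spacing is not evidence that readings were close together. Two a day is a goal; the same sentence allows different days, playback has only an upper limit, the care team could withhold reading, and two sets of parents made no recording. That mothers and fathers could read individually says who may read, not that two sessions took place on one day. The start-time distribution and the 80% power are assumptions. The 24-h spread, which fits the day-and-night wording better, gives only about 1–4%. The direction is towards no difference, so a before-versus-during benefit would not be created by it.

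Most of this stands, and it sets the size of the point. It does not remove the gap. Whatever happened in practice, the plan as written keeps another reading as control time, and the remedy is a small analysis step.

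A reader might infer that the control periods were in fact contaminated, or that the comparison is invalid. The document supports neither: it gives no reading times, and even the least favourable two-a-day setting leaves more than 90% of window time free of other reading on average.

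**Conclusion.** The gap is real and its likely effect is small. As written, a comparison period containing another live or recorded reading is used as control time, which pulls the contrast slightly towards no difference. With two readings every day at random times, the affected share is about 1–4% of window time over 24 h and at most about 7–8% with 60-min readings within 12 h. Fewer readings lower it, and deliberately spaced readings could bring it to zero; readings clustered around parent visits would raise it. The figures assume equal reading lengths, an equal effect of each reading and no carryover. The power values illustrate scale only, since the plan states none. This is a worthwhile, inexpensive improvement to the analysis and does not invalidate the study.

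**What to change.** Make the change in the analysis:

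1. Using the logged times of all live and recorded readings, remove from each comparison window the minutes that overlap another reading. The 5-second monitor download makes this feasible.
2. Express apnea, bradycardia and saturation <85% counts per minute of remaining window, and take mean heart rate and respiratory rate over the remaining minutes.
3. For variables collected per period (mode of respiratory support, supplemental oxygen), drop the overlapped window, because minutes cannot be removed from a single value.
4. State whether each time point is a block or a slot, since the overlap cannot be computed without it.
5. Report the number of windows and minutes removed at each of the three time points, and show the all-windows result as a check. A count of zero would settle the question.

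**Cost.** A little programming and, under the two-a-day assumption, about 1–8% of window time. For the per-period variables the loss is in whole windows: about 4–9% of 1-h blocks, and about 12–24% if the 3-h period is a block. The change depends on reading times having been logged. If they were not, the report should say so and give the range above as a limitation.

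### Apnea, bradycardia and SpO2 <85% counts are compared with no time denominator, and nothing makes the comparison windows as long as the reading

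*Combined protocol and SAP*

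**What the plan says.** The Combined protocol and SAP describes the comparison in two places.

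- The main Study Protocol paragraph states that "Cardiorespiratory events for each reading exposure were compared to the immediate period before and after the reading exposure", and that "the period before each reading exposure served as the control period for that reading exposure". It also gives the length requested of parents, "lasting a minimum of 15 min but up to 60 min of recorded reading"; the upper limit is worded for recordings. It does not give the length actually analysed.
- The paragraph on cardiorespiratory data lists the outcomes, among them "Mean RR, HR, apnea and bradycardia episodes" and "number of periods with oxygen saturation <85"%. These are "compared to the reading period at 3 time points: 3 h before reading, 1 h before reading and 1 h after reading". The only methods named are the χ² "test for categorical variables and student's t test for continuous variables".

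Neither place divides events by time or says that a reading and its comparator cover the same number of minutes. The word *period* is used in two ways. The oxygen data, for instance, cover the "amount of supplemental oxygen needed were collected for each time period", where it means an observation window. The desaturation outcome could therefore count episodes, or windows that contain at least one.

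**The concern.** A count of events grows with the time watched. A mean count per window does too, so it does not help if the word *mean* in the outcome list is taken to cover the episodes. The chance that a window contains any event, which a χ² test would compare, also grows with its length.

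If the comparison windows are longer than the reading, infants will appear to have fewer apneas, bradycardias and desaturations during reading even if reading does nothing. That error runs in favour of the intervention. A reader with only this document cannot tell whether a difference on these three outcomes reflects reading or minutes observed.

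Mean HR, mean RR, oxygen amount and mode of support are averages or states and do not scale with window length in this way.

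**Working it through.** The plan gives no event rate, sample-size calculation or expected difference, so there is no figure of its own to reproduce.

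**Inputs from the document.** Reading of 15 to 60 min (as requested); times of 3 h, 1 h and 1 h; significance at P<0.05 (two-sided assumed); 18 consenting sets of parents. The numbers of infants and of exposures analysed are not given.

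**Assumptions.** 0.5, 1 or 2 events per hour; 18 or 100 exposures; no effect of reading.

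**Step 1: what the stated times can mean.**

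- *Durations.* The windows are 180, 60 and 60 min. They differ from each other and, except for a 60-min reading against a 60-min window, from the reading. The 1 h windows then fit the description of an immediate period before and after most naturally.
- *Offsets*, as the term *time points* suggests. Where each window sits is then roughly known, but its length is not. Epochs matched to the reading are possible but not required.

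**Step 2: expected count ratio with no effect.** At a constant rate, ratio = reading minutes / comparator minutes.

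| Reading | 60-min comparator | 180-min comparator |
|---|---|---|
| 15 min | 15/60 = 0.25 | 15/180 = 0.08 |
| 30 min | 30/60 = 0.50 | 30/180 = 0.17 |
| 45 min | 45/60 = 0.75 | 45/180 = 0.25 |
| 60 min | 60/60 = 1.00 | 60/180 = 0.33 |

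The ratio is 1.0 whenever the lengths are equal.

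**Step 3: chance of any event.** P = 1 − exp(−rate × hours).

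| Rate | 15 min | 30 min | 60 min |
|---|---|---|---|
| 0.5/h | 12% | 22% | 39% |
| 1/h | 22% | 39% | 63% |
| 2/h | 39% | 63% | 86% |

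Dichotomising the counts therefore does not remove the dependence on length.

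**Step 4: what a t test would do.** Poisson counts were simulated with no effect, for 30 min of reading against 60 min. The event rate was either the same for every exposure, or varied between exposures (gamma, shape 1) and was shared by a reading and its comparator. The table gives the percentage of studies with P<0.05 and fewer events during reading, with 18 exposures.

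| Model and test | 0.5/h | 1/h | 2/h |
|---|---|---|---|
| Varying rate, unpaired | 12 | 17 | 24 |
| Varying rate, paired | 18 | 31 | 55 |
| Constant rate, unpaired | 21 | 39 | 67 |

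The nominal value in one direction is 2.5%. With 100 exposures the range over these models is roughly 72% to 100%. With equal windows (30/30 or 60/60 min) and 18 exposures, no model exceeded about 2.7%.

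**The case against.** The strongest reply is that no unequal comparison has been shown. Each reading has its own control period, and the term *time points* fits epochs of the reading's length taken at fixed offsets. *Mean* episodes could also have been intended as a rate per unit time. All of this is possible, and it is why the point is conditional. But the stated purpose of the own-control design is to deal with reading on different days and at different times. That addresses timing, not duration, and no time unit is attached to the episodes.

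Three stronger readings are tempting, and the document does not support them.

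- *That unequal windows were used and the results are biased.* The text leaves this open.
- *That no window length is stated at all.* The 3 h, 1 h and 1 h may be durations, and the reading has a requested range. The lengths are ambiguous, which is different from absent.
- *That one false-positive rate can be attached to the plan.* The figures move with the event rate, its variation between exposures, pairing and the number of exposures. Eighteen is a count of parent sets; with a goal of at least two readings a day, exposures may be far more numerous. For 45 against 60 min, the unpaired test with varying rates stays near nominal (about 2% to 4%), while the constant-rate model gives about 8% to 20%.

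The direction does not depend on these choices. At a constant rate, a comparator longer than the reading always lowers the expected count during reading relative to it.

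**Conclusion.** The concern holds in conditional form and should be fixed. As written, the plan lets a difference in apnea, bradycardia or desaturation counts arise from window length alone, and a reader cannot exclude it. Under the duration reading the lengths are unequal except for 60-min readings against the 1 h windows; under the offset reading they are unspecified.

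The count ratios need only a constant event rate and no effect. The test-level figure of about 12% to 67% is an illustration for 30 against 60 min with 18 exposures at 0.5 to 2 events/h, and should not be quoted as the error rate of this study. If the windows were in fact equal in length, no bias arises from this source. The point concerns three outcomes only.

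**What to change.** 1. State whether 3 h, 1 h and 1 h are offsets or durations, give the start and length of every window, and reconcile this with the description of an immediate period before and after.
2. Define a period with SpO2 below 85%: an episode (with its start and end rule) or a window containing one.
3. Make time comparable in one of two ways:
   - cut each comparator to the length of its own reading; or
   - analyse events per valid monitored hour, using a count model with log valid minutes as offset that accounts for repeated readings in the same infant.

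**Cost.** If length-matched windows were already used, one sentence saying so is enough on window length and the results do not change. Otherwise the windows must be re-extracted from the 5-second data already downloaded and three analyses rerun; no new data are needed. Shorter comparators contain fewer events, so power falls, and the apparent effect may shrink.

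### The two pre-reading windows are never compared with each other, so change that occurs without reading could go untested and be attributed to reading, above all in the comparison with 3 h before

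*Combined protocol and SAP*

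**What the plan says.** The Study Protocol describes the comparison in two places.

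- **First paragraph (design and control period).** Events during reading were "compared to the immediate period before and after the reading exposure", and "the period before each reading exposure served as the control period for that reading exposure". The stated purpose is "to mitigate the effect of reading on different days or time periods". A 3 h window is not mentioned here.
- **Second paragraph (data and analysis).** Outcomes were "compared to the reading period at 3 time points: 3 h before reading, 1 h before reading and 1 h after reading". The reason given is: "These time points were chosen to provide a variety of time periods in relation to care times and feedings". Monitor values "were continuously downloaded every 5 seconds directly from bedside GE monitors using BedMaster EX Software", and respiratory support and supplemental oxygen were collected for each period. The tests are chi-square and "student's t test for continuous variables", with P < 0.05 as the criterion.

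Neither paragraph plans a comparison of 3 h before with 1 h before, a time trend, or a session without reading. The length and exact position of each window are not given.

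**The concern.** Each infant is its own control, so the inference assumes that the outcome would have stayed at its pre-reading level had there been no reading. Using a control period from the same session deals with differences between days and between sessions. It does not deal with change within the few hours around one session. The plan itself makes such change plausible, because its windows were picked to fall at varied points relative to care and feeding.

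The comparison with 3 h before is the most exposed, because it spans the longest gap, yet the second paragraph gives it the same standing as the comparison with 1 h before. The two pre-reading windows could show how far an outcome moves with no reading in between, and the data for that check are already collected. Without it, a significant difference between reading and a before-window may be read as a reading effect when it reflects movement already under way.

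**Working it through.** The plan states no sample size calculation, effect size or SD, so there is no figure to reproduce. What follows is an illustration.

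**From the documents:** 18 sets of parents consented, and 2 of these sets made no recording (18 − 2 = 16). The significance level is 0.05. Windows are 3 h before, 1 h before and 1 h after reading.

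**Assumed, not in the documents:** 18 infants (16 as a sensitivity value); one value per infant per window; a paired, two-sided t test; windows at −3, −1 and 0 h; zero reading effect; linear drift of d per hour, in units of the between-infant SD of a window difference, taken as equal for all contrasts.

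**Step 1, gaps.** Reading versus 1 h before spans 1 h, reading versus 3 h before spans 3 h, and 3 h versus 1 h before spans 2 h. The expected standardised differences are therefore d, 3d and 2d.

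**Step 2, formula.** For a gap of g hours the noncentrality is λ = g·d·√n. The chance of P < 0.05 is Pr(|T| > t*), where T is noncentral t with n − 1 degrees of freedom and t* is the 97.5% point of central t (2.110 for n = 18; 2.131 for n = 16).

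**Step 3, worked example.** With n = 18 and d = 0.25, λ is 0.25 × √18 = 1.06, 0.75 × √18 = 3.18 and 0.50 × √18 = 2.12. The probabilities are 0.170, 0.850 and 0.516.

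**Step 4, range of drift.**

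| n | Drift (SD/h) | Reading vs 1 h before | Reading vs 3 h before | 3 h vs 1 h before (not planned) |
|---|---|---|---|---|
| 18 | 0.1 | 7% | 23% | 13% |
| 18 | 0.2 | 13% | 67% | 36% |
| 18 | 0.25 | 17% | 85% | 52% |
| 18 | 0.5 | 52% | >99% | 98% |
| 16 | 0.25 | 16% | 80% | 46% |

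The first two probability columns are false-positive rates, since the reading effect is zero. The last is the chance that the added contrast detects the drift.

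**Step 5, either before-comparison significant.** In a simulation of 40,000 trials (n = 18, independent window errors), reading differs significantly from at least one before-window in 9% of trials with no drift, 26% at 0.1 SD/h and 68% at 0.2 SD/h.

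**Step 6, what the added contrast misses.** If the outcome is level at −3 and −1 h and changes only at the time of reading for some other reason, the 3 h versus 1 h contrast is significant about 5% of the time, which is its nominal rate. It gives no warning of that kind of change.

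**The case against.** **The after-reading window already provides a check.** Both paragraphs plan a comparison with the period after reading. Steady drift should continue into that hour, and a return to the earlier level would argue against drift. This stands in part. But a lasting effect of reading would also show as a level that does not return, so the window cannot separate the two.

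**The pre-reading change can be read off the planned results.** Reading minus 3 h before, less reading minus 1 h before, equals 1 h before minus 3 h before. The point estimate is therefore recoverable from the window means. Its uncertainty is not recoverable from the two planned tests, which share the reading window, and no one is told to look at it.

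**The illustration builds in its answer.** Linear drift makes a 3 h gap three times as biased as a 1 h gap by construction, and change tied to care and feeding may be episodic. This stands: the percentages show what could happen and do not estimate what did. For the control named in the first paragraph the false-positive rate is 17%, not 85%.

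**The 3 h window may not be unexposed.** The goal is at least two reading episodes a day, and no minimum gap is stated. The wording also allows a 3-hour block that contains the 1 h window. This stands and has to be settled before the contrast can serve as a negative control.

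**Two stronger readings are tempting.** A reader might infer that drift did occur and was counted as a reading effect; the documents report no drift and state no rule for attributing differences. A reader might also adopt a rule that credits reading only when its difference exceeds, or runs opposite to, the change between the pre-reading windows. That rule sets a 1 h change against an unscaled 2 h change, and both share the 1 h window. In simulation at 0.25 SD/h with no reading effect, it lowers false positives against 1 h before only from 17% to 14%.

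**Conclusion.** The gap is real and limited. All planned contrasts involve the reading period, there is no separate control group, and no contrast or time term addresses change within the hours before a session. Change without reading could therefore go untested and be attributed to reading.

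The exposure is greatest for the 3 h comparison (85% false positives at 0.25 SD/h, against 17% for the 1 h comparison). These sizes rest on assumed linear drift, 18 infants, pairing and non-overlapping windows. The documents supply none of these, and they give no evidence on whether drift is present or how large it is. This should be corrected, but it does not by itself invalidate the comparison with the immediate pre-reading period.

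**What to change.** 1. Define the start, length and position of each window so that none overlap. Use the 3 h window only for sessions where no earlier reading falls in it.
2. Keep the immediate pre-reading period as the primary control, as the first paragraph states, and keep the after-reading comparison.
3. For each outcome, report the 3 h versus 1 h before difference with its confidence interval beside the reading effect, as a negative control.
4. Do not count a difference from 3 h before alone as evidence of a reading effect.
5. If adjustment is wanted, fit all windows together with infant and session effects and a time term, as a sensitivity analysis.

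The cost is one extra contrast per outcome on data already collected. Some sessions may lose their 3 h window, and the 3 h comparison no longer supplies a result of its own. The contrast has low power for small drift (13% at 0.1 and 36% at 0.2 SD/h with 18 infants), so a non-significant result is not proof of stability; hence the interval. It gives no protection against change tied to the moment of reading, such as a parent's presence or open portholes.

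### The χ² and Student's t tests are named without pairing or clustering, although each reading is its own control and readings repeat within infants

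*Combined protocol and SAP*

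**What the plan says.** The first paragraph of the Study Protocol describes a matched comparison: "Cardiorespiratory events for each reading exposure were compared to the immediate period before and after the reading exposure", and "the period before each reading exposure served as the control period for that reading exposure". It also points to several readings per infant. Reading was offered "with the goal of at least 2 reading episodes per day", live and recorded reading could fall on different days, and the notes on holding refer to one reading or one day among others. One of these notes says that "the infant was removed from the incubator and was being held for all comparison time points around that single reading exposure"; the other drops a single day for each of two babies. The number of infants and of readings per infant is not given. The count is of families: "Of 21 sets of parents approached, 18 consented to participate".

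The final paragraphs list the outcomes (respiratory rate, heart rate, apnea and bradycardia episodes, supplemental oxygen, mode of respiratory support, low-saturation periods) and three comparison points: 3 h before, 1 h before and 1 h after reading. The whole analysis is then given as "Results were compared using χ^2 test for categorical variables and student's t test for continuous variables", with P < 0.05 as the criterion. Pairing, a matched test for categorical data, a mixed model, GEE and infant-level summaries are not mentioned.

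**The concern.** Two features of the data are missing from the analysis.

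- **Matching.** The reading and its comparison periods come from the same infant on the same occasion. An ordinary χ² test treats them as independent groups. So does a t test unless it is paired, and the form used is not stated.
- **Repetition.** The text leans towards the single reading as the unit of comparison. If infants differ in how they respond, readings from one infant are correlated, and a t test paired by reading overstates the information.

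The two omissions pull in opposite directions. Ignoring matching makes a test conservative when stable differences between infants dominate; ignoring repetition makes it liberal. A significant result could be a false positive, and a null result could reflect lost power. Because one sentence covers every outcome at all three comparison points, every P-value is affected.

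**Working it through.** **No figure to reproduce.** The plan gives no sample size calculation, effect size, SD or correlation. The only number to test is the 0.05 threshold, taken as two-sided.

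**Inputs.** From the plan: 18 families, matched periods, repeated readings. Assumed: 18 infants; m readings each (1 to 20); heart-rate SD between infants B = 5, 10 or 15 bpm; SD 5 between days, shared by a reading and its comparison period; SD 4 within a period; between-infant SD of the reading effect τ = 0, 1, 2 or 4 bpm.

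**Step 1: infant means.** One reading-minus-control difference has variance τ² + 2×4² = τ² + 32. The mean over 18 infants has variance (τ² + 32/m)/18, which a one-sample t on infant means (17 df) estimates directly. Simulated type I error is 4.5–5.4% in all heart-rate settings (10,000 replicates each).

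**Step 2: t paired over all readings.** This test assumes variance (τ² + 32)/(18m). The ratio of true to assumed variance is k = 1 + (m − 1)·ICC, with ICC = τ²/(τ² + 32), and the actual level is about 2[1 − Φ(1.96/√k)]. For m = 6, τ = 4: ICC = 16/48 = 0.333, k = 1 + 5×0.333 = 2.667, level 0.23. For m = 10, τ = 2: ICC = 4/36 = 0.111, k = 2.0, level 0.17. Simulation agrees:

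| Readings per infant | τ = 0 | τ = 1 | τ = 2 | τ = 4 |
|---|---|---|---|---|
| 1 | 5% | 5% | 5% | 5% |
| 3 | 5% | 6% | 8% | 13% |
| 6 | 5% | 7% | 11% | 23% |
| 10 | 5% | 8% | 17% | 33% |
| 20 | 5% | 12% | 27% | 48% |

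**Step 3: unpaired t over all readings.** Now k = (32 + mτ²)/[2(B² + 25 + 16) + τ²].

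- B = 10, τ = 0: k = 32/282 = 0.113, level near 0.
- B = 10, τ = 4, m = 20: k = 352/298 = 1.18, level 7% (8% simulated).
- B = 5, τ = 4, m = 20: k = 352/148 = 2.38, level 20% (21% simulated). At m = 10: k = 192/148 = 1.30, level 8.5% (9.5% simulated).

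With B = 10 and up to 10 equal readings, the simulated level is 0–2.2%.

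**Step 4: power for a 2 bpm effect, 6 readings.** The infant-level standard error is √[(τ² + 32/6)/18], which is 0.544 at τ = 0 and 1.089 at τ = 4. Power is 93, 89, 74 and 41% at τ = 0, 1, 2, 4. The unpaired t has 38–41%, 5–15% and 0.3–3% at B = 5, 10 and 15.

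**Step 5: other parameters.** With variances set through assumed correlations instead (18 infants, 2 to 20 readings), type I error was 0–26.8% unpaired, 4.6–47.7% paired by reading and 4.2–5.6% at infant level.

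**Step 6: episode counts by t test.** Assuming periods of equal length, mean 0.5–4 episodes, 3–10 readings and log-rate effect SD 0, 0.3, 0.6: unpaired 0–3.5%, 0.2–8%, 2–30%; paired by reading 4–5%, 5–28%, 7–44%; infant-level 2.7–5.3% overall.

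**Step 7: mode of respiratory support.** This is the one plainly categorical outcome: "The data on mode of respiratory support and amount of supplemental oxygen needed were collected for each time period". With three levels, 3–10 readings and random mode changes in 2–20% of exposures, χ² rejects 0–0.1% under the null. If 5, 10 or 20% of exposures move one level, χ² power is 0–0.3%, 0–6.5% and 0.2–62%, against 2–39%, 7–75% and 20–97% for an infant-level t on proportions. That t test is itself sometimes conservative (0–5.5% under the null).

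**Step 8: siblings, if any.** Multiple birth is not a listed exclusion. With 4 twin pairs among 18 families (sibling effect correlation 0.5–1, τ = 1–4), the infant-level t gives 5–9%; averaging by family gives 4.7–5.3%.

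**The case against.** A paired t test is a Student's t test, and the protocol says each reading has its own control period, so pairing is a natural reading of a short, past-tense summary. For continuous outcomes this half of the point may be a gap in description that one sentence could close. The clustering half depends on the number of readings per infant, which is not given. At 3 readings the error of the reading-paired test is only 5, 6 and 8% for τ up to 2; the 23–48% figures need 6 to 20 readings and τ = 4, twice the 2 bpm effect used for power. For mode of support, χ² costs power and does not create false claims. Nothing shows that siblings were enrolled.

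Most of this stands as a limit on size: the figures are ranges over assumptions, and the likely error in this study cannot be identified. It does not remove the fault. Pairing by reading, the version the text best supports, still leaves repeated readings unaddressed. Only pairing on infant means would be sound, and that is not described. The ordinary χ² test is unsuitable for matched periods under any reading.

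**Conclusion.** The concern holds and must be fixed before the P-values are relied on. The named χ² test does not fit the design. The t test as described does not establish a 5% level, because it could be any of three materially different analyses.

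Direction and size are unknown. With one reading per infant or a homogeneous effect, a t test paired by reading keeps about 5%; with more readings and varied response it is liberal. An unpaired t test is usually conservative and low in power here, but turns liberal with many readings and strongly varying response. Confidence is high that the omission is real and that infant-level analysis cures it. No such confidence attaches to any single error rate, since the number of infants, readings, SDs, event rates and correlations are all assumed.

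**What to change.** - State the infant as the unit of analysis. For each outcome and comparison point, take reading minus comparison period within each exposure, average per infant, and apply a one-sample t or Wilcoxon signed-rank test to the infant means. The signed-rank test held 4.2–5.5% in the heart-rate settings. A mixed model with an infant-by-period effect, or GEE with a small-sample correction, is an acceptable alternative.
- Express episode and desaturation counts as rates per unit time, since readings ran from 15 to 60 min, and analyse them the same way.
- Replace χ² for mode of support by the per-infant proportion of exposures at each level, or report it descriptively if few infants change mode.
- Average or cluster by family if siblings were enrolled. Show live and recorded reading separately as well, since two families made no recording.
- Report the numbers of infants, families and readings per infant.
- If the t test was already paired on infant means, say so. Only the variables tested by χ² then need re-running, possibly mode of support alone.

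**Cost.** Revised wording and a small re-analysis of data already in the spreadsheet. Some P-values may become less favourable. Equal weighting loses power when readings are very unequal: for 2 bpm at τ = 1, 70% with 9 infants at 2 readings and 9 at 10, against 88–89% with 6 each. A random-effects weighted mean of the infant means (Hartung-Knapp variance, n − 1 df) recovers this to 86%. Its type I error is 4.8–5.8% in that split, and up to 6.5% with 6 infants each at 1, 3 and 14 readings.
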